4.6. Analysis Visit Windows

Each visit will be denoted by its “month” and “day” such that the first dose day is denoted as Month 1-Day 1; subsequent months will use sequential numbers (e.g., the second dose is administered on Month 2-Day 1). Each infusion is scheduled to be every 28 days (± 5 days) based on the first infusion date. For reporting purposes, the nominal visits will be used for the by-visit analyses. Details of the protocol defined visits and visit windows are given in the protocol and [Table 1](#). In the event of unscheduled visits, re-test assessments, or ETD assessments, these will be reassigned to a scheduled visit for analysis purposes according to [Tables 2, 3, 4 and 5](#).

below. If multiple visits occur within a single visit window, after reassignment of unscheduled visits and ETD visits, then the visit closest to the target day of the visit window will be used in the analysis. If there is a tie, the later visit will be used in the analysis. Unscheduled assessments that do not collect time will not be mapped to any scheduled visit/timepoint.

In data listings, the relative study day from first infusion of all dates will be presented.

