3. Study visits will occur every 28 days based on scheduling from Month 1-Day 1. A ± 5 -day window is allowed for visits starting after Month 1. The predose assessments for each visit may be performed within the 3 days before the visit unless a different timeframe is specified in Section 6.1.
4. Conduct the EOS Visit 30 (± 5) days after last administration of study drug. Subjects who discontinue study drug before the end of the study should have an ETD Visit 30 (± 5) days after their final administration of study drug. The assessments shown for EOS/ETD should also be conducted for any unscheduled visit (i.e., a visit not specified by the protocol) as clinically indicated or if deemed necessary.
5. Medical History - Obtain medical history since the subject's last visit in Study NEOD001-201 (including all major hospitalizations and surgeries), as well as the subject's current medical status and therapy for AL amyloidosis.
6. Record all prior/concomitant medications taken or received by a subject within the 28 days prior to the Month 1-Day 1 Visit through the EOS/ETD Visit, and any changes to concomitant medications during the study.
7. Adverse events will be collected from the time that the ICF is signed through 30 days after the last dose of study drug or last study visit, whichever is later.
8. **Screening and EOS/ETD:** conduct a complete physical examination per Section 6.5.1.3. **All Other Visits:** conduct a directed physical examination per Section 6.5.1.3.
9. Vital signs (HR, BP, RR, and body temperature) - collect after the subject has been at rest for ≥ 5 minutes; within a visit, assess in the same position for all time points. **Month 1:** Within 30 minutes before start of dosing, at EOI (+5 minutes), 30 (± 5) minutes after EOI, and 60 (± 10) minutes after EOI. **All Other Months:** Within 30 minutes before start of dosing, at EOI (+5 minutes), and 60 (± 10) minutes after EOI.
10. See Appendix 4 (ECOG) and Appendix 5 (NYHA).
11. See Appendix 6; NIS-LL is for all subjects who had peripheral neuropathy in Study NEOD001-201.
12. See Appendix 7; VASPI is for subjects who had painful peripheral neuropathy in Study NEOD001-201.
13. See Appendix 8; SF-36v2 should be administered before performing any other study assessments on the same calendar day it is administered.
14. See Appendix 9; administer KCCQ after the SF-36v2, but before conducting any other assessments on the same calendar day it is administered.

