15. NT-proBNP should be drawn before conducting 6MWT if being performed on the same calendar day.
16. Collect blood pressure and heart rate pre- and post-6MWT administration.
17. Two pretreatment 6MWTs are required before the first administration of study drug, with a minimum of 4 days between the two tests. The first Screening 6MWT is required to be performed between Days -28 and -5, at least 4 days prior to the second Screening 6MWT, which should be performed within 2 days prior to Month 1-Day 1 (i.e., on Day -2 or Day -1).
18. The postbaseline 6MWTs may be administered on the same calendar day that study drug is administered as long as the NT-proBNP sample is drawn before conducting the 6MWT and the 6MWT is completed before initiation of the study drug infusion.
19. Perform ECGs centrally within 30 minutes before start of dosing and within 15 minutes after EOI.
20. All laboratory tests to be done centrally, unless otherwise noted. Please refer to Laboratory Manual for details. Laboratory tests conducted within 28 days of Month 1-Day 1 may be used for screening.
21. Hematology and chemistry per Appendix 10. Within 3 days before the first day of a new regimen of chemotherapy, conduct an unscheduled central laboratory collection (including hematology, chemistry, PT/INR, and PTT).

22. Collect citrated plasma samples, which will be frozen for potential analysis of coagulation indices at a later date; see [Appendix 11](#). **Month 1:** EOS/ETD results from Study NEOD001-201 will serve as baseline for this study. Collect sample for vWF activity and antigen assays before dosing on Month 1-Day 1 if they were not tested at EOS/ETD in Study NEOD001-201. **Month 12:** Subjects with defects identified at EOS/ETD in Study NEOD001-201: collect sample and test analytes that were abnormal. All other subjects: collect sample. **EOS/ETD:** Subjects with defects identified at Month 12: collect sample and test analytes that were abnormal. All other subjects: collect sample. **Unscheduled Samples:** collect sample in case of relevant serious adverse events. At any time, if defects are identified, additional analytes will be evaluated, as indicated.
23. Urine pregnancy tests (local) for WOCBP: **Screening:** within 28 days before Month 1-Day 1; **Monthly:** preinfusion; **EOS/ETD:** any time during visit. A positive urine pregnancy test (local laboratory) is to be confirmed with a serum pregnancy test (central laboratory).

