4.6.2. OLE Therapy Visit Windows

Table 4 defines the visit windows for assessments taken at 1-month intervals to be established with respect to relative day from the start of NEOD001 therapy in the OLE.

Table 4: OLE Therapy 1-Month Interval Visit Windows (Days)

Months	Target Study Day ^a	Analysis Window Study Day ^a	
		Low	High
OLE Baseline ^b	1	Closest visit to Day 1, prior to first OLE NEOD001 dose	
OLE Month 2	28	14	42 [= 28 + 28/2]
OLE Month 3	56	43 [= (28 + 28/2) + 1]	70 [= 56 + 28/2]
OLE Month x	28*x	(x-2)*28 + 28/2 + 1	(x-1)*28 + 28/2

OLE = open-label extension.

^a Study day will be calculated from first OLE dose date.

^b OLE Baseline is defined in Section 2.2.4.2.

Table 5 defines the visit windows for assessments taken at 3-month intervals to be established with respect to relative day from the start of NEOD001 therapy in the OLE.

Table 5: OLE Therapy 3-Month Interval Visit Windows (Days)

Months	Target Study Day ^a	Analysis Window Study Day ^a	
		Low	High
OLE Baseline ^b	1	Closest visit to Day 1, prior to first OLE NEOD001 dose	
OLE Month 3	56	14	98 [= 56 + 84/2]
OLE Month 6	168	99 [= (56 + 84/ 2) +1]	182 [= (140 + 84/2)]
OLE Month x	28*x	$(x-4)*28 + 84/2 + 1$	$(x-1)*28 + 84/2$

OLE = open-label extension.

^a Study day will be calculated from first OLE dose date.

^b OLE Baseline is defined in Section 2.2.4.

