8. EFFICACY ANALYSES

All recorded efficacy endpoint data will be presented in by-subject data listings for the OLE Safety Population.

Analyses will be produced in both NEOD001 Safety Population and OLE Safety Population, unless otherwise specified. Data, visit window, and treatment group to be used for each population as below:

1. NEOD001 Safety Population:
 - Data: Pooled data from parent and OLE study
 - Visit window: PRONTO visit window for data in parent study, OLE therapy visit window for OLE data with exclusion of OLE Baseline.
 - Treatment: Placebo and NEOD001 subjects received in NEOD001-201 study and Overall
2. OLE Safety Population:
 - Using data from OLE study only
 - Visit window: OLE therapy visit window
 - Treatment: NEOD001

Analyses in Renal Evaluable Population or Peripheral Neuropathy Evaluable Population will be presented in the same manner described above for NEOD001 Safety Population and OLE Safety Population.

Baseline in all efficacy analyses refers to PRONTO Baseline and OLE Baseline, unless otherwise specified.

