8.6.3. NT-proBNP Endpoint: Change from Baseline

Change from baseline will be analyzed using a REML based MMRM model including a fixed effect for categorical time point and with the baseline value included as a covariate. The unstructured covariance model will be used. If the computational algorithm fails to converge, the following structures will be executed: heterogeneous Toeplitz, Toeplitz, heterogeneous First-Order Autoregressive [AR(1)], AR(1), heterogeneous compound symmetry (HCS), and compound symmetry (CS). The covariance structure converging to the best fit, as determined by Akaike’s information criterion (AIC), will be used. The Kenward and Roger method will be used to calculate the denominator degrees of freedom for the test of fixed effects. All visits will be

included in the model. Estimates of least-square (LS) means, standard errors (StdErr), and 95% CIs will be presented at each visit.

Descriptive statistics for NT-proBNP, change from baseline, and percent change from baseline will be presented by visit.

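### The OLE target day `28*x` (and the 168 printed for Month 6 in SAP Table 5) is 28 days too late, so on the rule as written a later extra record displaces the scheduled value.

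*SAP*

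**What the plan says.** SAP 4.6 takes nominal visits as the basis for by-visit analyses and then adds a mapping step: "In the event of unscheduled visits, re-test assessments, or ETD assessments, these will be reassigned to a scheduled visit for analysis purposes" using Tables 2 to 5. If a window then holds several visits, "then the visit closest to the target day of the visit window will be used in the analysis"; a tie goes to the later one. One limit applies: "Unscheduled assessments that do not collect time will not be mapped to any scheduled visit/timepoint".

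Table 4 (monthly items in the OLE) prints targets of Day 28 for Month 2 and Day 56 for Month 3, then `28*x` for Month x. The generic window in that row runs from 28(x−2)+15 to 28(x−1)+14. Table 5 "defines the visit windows for assessments taken at 3-month intervals". It prints Day 56 for Month 3, Day 168 for Month 6 with an upper limit derived as 140 + 84/2 = 182, and again `28*x` for Month x. The parent-study tables (Tables 2 and 3) give 140, 224 and 308 for Months 6, 9 and 12.

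SAP 8 assigns these windows to the OLE Safety Population ("Visit window: OLE therapy visit window") and also to the OLE portion of the pooled data in the NEOD001 Safety Population.

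**The concern.** The generic target disagrees with the printed rows above it and with the window limits beside it. Because the target decides which of several records is analysed, this changes the data selected and is more than a labelling slip. A target beyond the end of the window makes every later day closer than every earlier one, so the rule becomes: take the last mapped record.

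Competing records are foreseeable and need not be random:

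- Protocol Table 1, footnote 4: "The assessments shown for EOS/ETD should also be conducted for any unscheduled visit", where clinically indicated or judged necessary. Those assessments include NT-proBNP, so extra values can come from visits made for deterioration.
- Protocol Appendix 3, footnote a: cardiac progression must be confirmed by a repeat assessment. A repeat in the same window would displace the value that prompted it.
- Protocol Table 1, footnote 21: "Within 3 days before the first day of a new regimen of chemotherapy, conduct an unscheduled central laboratory collection". This collection includes chemistry, so it reaches creatinine and eGFR but not NT-proBNP.
- Protocol 5.4.1: central laboratory tests are repeated if drawn more than 7 days before a rescheduled dose.

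The exposed analyses are NT-proBNP response at each visit (SAP 8.6.2), the NT-proBNP MMRM and by-visit summaries (SAP 8.6.3: "Descriptive statistics for NT-proBNP, change from baseline, and percent change from baseline will be presented by visit"), creatinine and eGFR (SAP 8.9.3), and by-visit renal response (SAP 8.9.2) through its eGFR component. In the pooled population, parent-study records would be selected around 28(x−1) and OLE records around a day 28 days later, within one analysis.

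**Working it through.** **Inputs.** First dose is Month 1-Day 1, with visits every 28 days ±5 (SAP 4.6). The first OLE dose is study Day 1 (SAP 4.1), so Month x is due on Day 28(x−1)+1. Targets and limits are from SAP 4.6.1 and 4.6.2.

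**1. Reproducing the printed figures.** The window formulas work: Table 4 at x = 3 gives 43–70 as printed, x = 4 gives 71–98 (equal to PRONTO Month 4), and Table 5 at x = 6 gives 99–182 as printed. The target formula does not. `28*x` gives 56 and 84 for Months 2 and 3, printed as 28 and 56. 28(x−1) gives 28, 56 and, for Month 6, 140. The printed 168 is 28 × 6, so it comes from the same wrong formula.

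**2. Table 4 target against its own window.** 28x − [28(x−1) + 14] = 14 for every x.

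| Month | Window | Printed target | Days past upper limit | 28(x−1) |
|---|---|---|---|---|
| 4 | 71–98 | 112 | 14 | 84 |
| 6 | 127–154 | 168 | 14 | 140 |
| 12 | 295–322 | 336 | 14 | 308 |
| 36 | 967–994 | 1008 | 14 | 980 |

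**3. One example, Month 6.** Scheduled visit on Day 141, unscheduled draw on Day 150.
- As printed (168): distances 27 and 18; the draw is used.
- Corrected (140): distances 1 and 10; the visit is used.

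For an on-time visit, all 13 later days in the window displace it as printed. None does with 28(x−1), where later days are 2 to 14 days from target and the visit is 1.

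**4. Whole visit window.** For visits at −5 to +5 days, the later days left in the window number 18, 17, …, 8, total 143.
- As printed, a later record wins in 143 of 143 and an earlier one in 0 of 154 (9 + 10 + … + 19).
- Corrected, a later record wins in 8 + 6 + 4 + 2 = 20 of 143 (14%) and an earlier one in 1 + 3 + 5 + 7 + 9 + 11 = 36 of 154 (23%).

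The corrected rule selects from both sides; the printed one is wholly one-sided. These are day combinations, not patients or visits.

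**5. Table 5.** The Month 6 target of 168 lies inside 99–182, but a visit on Day 141 is 27 days away and all 41 later days (142–182) are closer. With 140, none of the 41 is.

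**6. ETD records.** Under Table 4, an ETD 25 to 35 days after an on-time last dose falls on Days 28(x−1)+26 to 28(x−1)+36. This is inside the Month x+1 window, 28(x−1)+15 to 28(x−1)+42, in all 385 combinations (35 months × 11 days). It normally meets no scheduled value there. The exception is a Month x+1 visit completed with the dose withheld (Protocol 5.4.1), which a later ETD in that window would displace. If Table 5 governed the 6-monthly items at Months 6, 12, 18, 24 and 30, an ETD after a last dose in those months would displace the scheduled value in 55 of 55 combinations (5 × 11) as printed and 0 of 55 corrected. The SAP does not say that it does.

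**The case against.** The window limits are right, so no record goes to the wrong month. Only the choice among several records in one window is affected, and untimed unscheduled assessments are never mapped. The documents give no count of competing records, so the effect on any estimate is unknown. This stands, and it limits what can be claimed about size.

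The reliance on nominal visits in SAP 4.6 could be read as protecting the scheduled value, with the target used only to choose among reassigned records. That reading is possible but not the literal one: the closest-to-target step is applied after reassignment and gives the nominal visit no precedence. The sentence that sets that step names unscheduled and ETD visits but not re-tests, so displacement by a re-test is inferred from the mapping sentence before it.

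The OLE has no concurrent control and no multiplicity-controlled claim, and an alert programmer may notice a target outside its window. SAP 10 also records that the program was discontinued, so Months 4 to 36 is the maximum range over which the formula operates. These points lower the stakes. They do not make the printed formula right, and a programmer who silently used another would be departing from the SAP.

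**Conclusion.** The error is real and should be fixed. The generic OLE target is 28 days later than the SAP's own convention (27 days later than the due day under Day 1 numbering). In Table 4 it falls 14 days outside its window for every month the generic row governs, Months 4 to 36. Applied literally, any later mapped record in the window replaces the scheduled value in the monthly NT-proBNP, creatinine and eGFR by-visit analyses, in both analysis populations.

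This rests on two assumptions: that selection follows reassignment with no precedence for the nominal visit, and that the later record is one the SAP maps. Best response is unaffected because SAP 8.6.1 uses all visits after the first infusion. Survival and TEAE summaries do not use the windows. The 3-monthly items under Table 5 (ECG, anti-NEOD001) are only listed, so for efficacy Table 5 matters only if it is applied to the 6-monthly items.

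**What to change.** In SAP 4.6.2, replace the target `28*x` with 28(x−1) in the generic rows of Tables 4 and 5, and change the Table 5 Month 6 target from 168 to 140. This agrees with the printed Month 2 and 3 rows, the window limits and Tables 2 and 3. It costs two formula cells and one number, plus an update to the derivation program if it coded `28*x`. No data collection changes. One added sentence naming the table for the 6-monthly items (SF-36v2, 6MWT, NIS-LL, proteinuria) would be a useful clarification, but the correction does not depend on it.

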4.6.1. PRONTO Visit Windows

PRONTO visit windows, as defined in PRONTO SAP, will be used to map the data collected in parent study (NEOD001-201).

[Table 2](#) defines the visit windows for assessments taken at 1-month intervals to be established with respect to relative day from the start of study drug in parent study.

Table 2: PRONTO 1-Month Interval Visit Windows (Days)

Months	Target Study Day ^a	Analysis Window Study Day ^a	
		Low	High
PRONTO Baseline ^b	1	Closest visit to Day 1, prior to first NEOD001 dose	
PRONTO Month 2	28	14	42
PRONTO Month 3	56	43	70
PRONTO Month 4	84	71	98
PRONTO Month 5	112	99	126
PRONTO Month 6	140	127	154
PRONTO Month 7	168	155	182
PRONTO Month 8	196	183	210
PRONTO Month 9	224	211	238
PRONTO Month 10	252	239	266
PRONTO Month 11	280	267	294

Months	Target Study Day ^a	Analysis Window Study Day ^a	
		Low	High
PRONTO Month 12	308	295	319 [EEOS Low – 1]
PRONTO EEOS ^c	338	320 [Month 12 Low + 30 – 5]	

^a Study day will be calculated from first dose date in parent study.

^b PRONTO Baseline is defined in Section 2.2.4.

^c PRONTO EEOS is defined as the visit occurring 30 (-5) days after the Month 12 infusion in parent study.

Table 3 defines the visit windows for assessments taken at 3-month intervals to be established with respect to relative day from the start of study drug in parent study.

Table 3: PRONTO 3-Month Interval Visit Windows (Days)

Months	Target Study Day ^a	Analysis Window Study Day ^a	
		Low	High
PRONTO Baseline ^b	1	Closest visit to Day 1, prior to first NEOD001 dose ^b	
PRONTO Month 3	56	14	98
PRONTO Month 6	140	99	182
PRONTO Month 9	224	183	266
PRONTO Month 12	308	267	319 [EEOS Low – 1]
PRONTO EEOS ^c	338	320 [Same definition as table 3]	

^a Study day will be calculated from first dose date in parent study.

^b PRONTO Baseline is defined in Section 2.2.4.1

^c PRONTO EEOS is defined as the visit occurring 30 (-5) days after the Month 12 infusion in parent study.

4.6.2. OLE Therapy Visit Windows

Table 4 defines the visit windows for assessments taken at 1-month intervals to be established with respect to relative day from the start of NEOD001 therapy in the OLE.

Table 4: OLE Therapy 1-Month Interval Visit Windows (Days)

Months	Target Study Day ^a	Analysis Window Study Day ^a	
		Low	High
OLE Baseline ^b	1	Closest visit to Day 1, prior to first OLE NEOD001 dose	
OLE Month 2	28	14	42 [= 28 + 28/2]
OLE Month 3	56	43 [= (28 + 28/2) + 1]	70 [= 56 + 28/2]
OLE Month x	28*x	(x-2)*28 + 28/2 + 1	(x-1)*28 + 28/2

OLE = open-label extension.

^a Study day will be calculated from first OLE dose date.

^b OLE Baseline is defined in Section 2.2.4.2.

Table 5 defines the visit windows for assessments taken at 3-month intervals to be established with respect to relative day from the start of NEOD001 therapy in the OLE.

Table 5: OLE Therapy 3-Month Interval Visit Windows (Days)

Months	Target Study Day ^a	Analysis Window Study Day ^a	
		Low	High
OLE Baseline ^b	1	Closest visit to Day 1, prior to first OLE NEOD001 dose	
OLE Month 3	56	14	98 [= 56 + 84/2]
OLE Month 6	168	99 [= (56 + 84/ 2) +1]	182 [= (140 + 84/2)]
OLE Month x	28*x	$(x-4)*28 + 84/2 + 1$	$(x-1)*28 + 84/2$

OLE = open-label extension.

^a Study day will be calculated from first OLE dose date.

^b OLE Baseline is defined in Section 2.2.4.

5. ANALYSIS POPULATIONS

The NEOD001 Safety Population will include all subjects who received any amount of NEOD001 in the original parent study (NEOD001-201).

The OLE Safety Population will include all subjects who received any amount of NEOD001 in the OLE study.

The Renal Evaluable Population will include subjects who were in the Renal Evaluable Population in the original parent study (NEOD001-201), defined as subjects who had proteinuria >0.5g/24 hours (measured by 24-hour urine total protein excretion), at baseline and at least one post-baseline assessment of proteinuria in NEOD001-201.

The Peripheral Neuropathy Evaluable Population will include subjects who were in the in the Peripheral Neuropathy Evaluable Population in the original parent study (NEOD001-201), defined as subjects who had ascending sensorimotor neuropathy due to AL amyloidosis etiologies at screening, had a baseline Neuropathy Impairment Score–Lower Limbs (NIS-LL) total score of 2 or greater and at least one post-baseline NIS-LL total score in NEOD001-201.

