2.3.2.6. Time to All-Cause Mortality (Overall Survival)

Any deaths after the first infusion of study drug (i.e. study day 1) through the study's last subject last visit (LSLV). Time (months) to event will be calculated as: (date of death - the date of first study drug infusion + 1) / 30.4375. Subjects will be censored at their last assessment known to be alive prior to LSLV.

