4. GENERAL STATISTICAL METHODS

4.1. Reporting Conventions

Individual subject data obtained from electronic case report forms (eCRFs), central laboratories, external sources, and any derived data will be presented in data listings by subject. The primary data source will be used for all analyses. All data listings that contain an evaluation date will contain a relative study day. Pre-treatment and on-treatment study days are numbered relative to the day of the first dose of study drug in the OLE which is designated as Day 1. The preceding day is Day -1, the day before that is Day -2, etc.

All output will be incorporated into Microsoft Word rich text format (.rtf) files, sorted and labeled according to the International Council for Harmonisation (ICH) recommendations, and formatted to the appropriate page size(s).

For categorical variables, summary tabulations of the number and percentage of subjects within each category (with a category for missing data) of the parameter will be presented. Percentage calculations will be based on non-missing data, unless otherwise specified. Percentages are rounded to 1 decimal place, unless otherwise specified.

For frequency counts of categorical variables, categories whose counts are zero will be displayed for the sake of completeness. For example, if none of the subjects discontinued due to “lost to follow-up,” this reason will be included in the table with a count of 0. Percentages based on frequency counts will be presented to one decimal place, and values less than 1% will be presented as “<1%.” Values less than 100% but greater than 99% will be presented as “>99%.”

For continuous variables, the number of subjects, mean, standard deviation (SD), median, 25th quartile (Q1), 75th quartile (Q3), minimum, and maximum values will be presented. The precision of summary statistics, unless otherwise specified will be as follows: mean and median to 1 more decimal place than the raw data, and SD to 2 decimal places more than the raw data. In general, the number of decimal places should not exceed 3 decimal places unless appropriate. Confidence intervals (CIs) will be provided and will be rounded to 1 decimal place, unless otherwise specified, in the table and listing shell.

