7. STUDY POPULATION

7.1. Subject Disposition

Subject disposition will be tabulated for all screened subjects and will include:

- the number of subjects dosed in the original parent study (NEOD001-201; NEOD001 Safety Population)
- the number of subjects screened in the OLE
- the number screened but not enrolled in the OLE
- the number enrolled in the OLE (OLE Safety Population)
- the number in each organ evaluable population
- the number who discontinued treatment early in the OLE and reason(s) for discontinuation of treatment as recorded on the OLE eCRF
- the number who withdraw from OLE study prior to completing the study and reason(s) for withdrawal as recorded on the OLE eCRF

By-subject data listings of all the above study disposition data including study completion and any reasons for premature treatment and/or study withdrawal will be presented.

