8.2.1. Time to All-Cause Mortality

Subjects with no data after randomization will be censored on Day 1 (first day of study drug dosing).

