8.11. All-Cause Mortality (Overall Survival)

Overall survival, time to all-cause mortality, will be calculated in days as the date of death minus the date of first NEOD001 infusion plus 1. Subjects will be censored at their last assessment known to be alive prior to LSLV. Refer to [Section 8](#) for details about course of the study and relative first infusion of study drug for each set of analysis.

Kaplan-Meier (KM) estimates of the distribution of the time-to-event will be tabulated. The tabulation will include the KM estimate of the medians, 25th and 75th quartiles, and corresponding 95% CIs, if estimable. The number and percent of subjects censored and with events will be presented.

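### The pooled set admits only subjects given NEOD001 in PRONTO, so its required Placebo column is empty, and the SAP gives that set no single survival origin

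*SAP*

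**What the plan says.** **Who is in the pooled set**

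- SAP 5: "The NEOD001 Safety Population will include all subjects who received any amount of NEOD001 in the original parent study (NEOD001-201").
- SAP 8 assigns this set the combined parent and extension data and specifies its columns: "Treatment: Placebo and NEOD001 subjects received in NEOD001-201 study and Overall".
- SAP 7.1 glosses the same named set differently: "the number of subjects dosed in the original parent study (NEOD001-201; NEOD001 Safety Population").
- Protocol 1.2.2 records that blinded study drug in NEOD001-201 (PRONTO) was NEOD001 or placebo.

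**Where survival time starts**

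- SAP 2.3.2.6: "Any deaths after the first infusion of study drug (i.e. study day 1"), with time counted from the first study drug infusion.
- SAP 4.1 numbers study days "relative to the day of the first dose of study drug in the OLE which is designated as Day 1".
- SAP 8.11: survival "will be calculated in days as the date of death minus the date of first NEOD001 infusion plus 1". It refers the reader to Section 8 for the relevant first infusion.
- SAP 8.2.1: "Subjects with no data after randomization will be censored on Day 1 (first day of study drug dosing").
- SAP 4.6.1, Tables 2 and 3, describe PRONTO Baseline as "Closest visit to Day 1, prior to first NEOD001 dose". SAP 2.2.4.1 ties the same baseline to the first infusion of parent-study drug, whichever drug that was.

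**The concern.** The Section 5 definition and the Section 8 column layout cannot both be followed. A population flag is normally programmed from Section 5. Programmed that way, the pooled outputs for NT-proBNP, SF-36v2 PCS, 6MWT and overall survival would contain no parent-placebo subjects. These are the only planned efficacy displays that separate subjects by parent-study treatment.

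The survival origin is a second fault that the first one hides. While the set holds only NEOD001 recipients, the first parent infusion and the first NEOD001 infusion fall on the same date. Once placebo recipients are admitted, as Section 8 requires, the dates separate. Section 8.11 would then count the two columns from different points. It would count PRONTO deaths in the NEOD001 column and give PRONTO deaths on placebo no starting date.

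**Working it through.** The plan states no sample size, event count or survival assumption, so there is no figure to reproduce. The check has three steps: set membership, the origin under each rule, and date arithmetic.

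**Step 1. Membership** (assuming no placebo subject was given NEOD001 in error)

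| Parent treatment | Entered extension | In set by SAP 5 | In set by SAP 7.1 |
|---|---|---|---|
| NEOD001 | yes | yes | yes |
| NEOD001 | no | yes | yes |
| Placebo | yes | no | yes |
| Placebo | no | no | yes |

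Under SAP 5 the Placebo column has N=0 and Overall equals NEOD001. Under SAP 7.1 both placebo types enter. The documents give no PRONTO counts by arm, so the corrected N cannot be computed.

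**Step 2. Survival origin under each rule**

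| Parent treatment, extension entry | 2.3.2.6, first parent infusion | 2.3.2.6, Day 1 as in 4.1 | 8.11 |
|---|---|---|---|
| NEOD001, yes | first PRONTO infusion | first extension infusion | first PRONTO infusion |
| NEOD001, no | first PRONTO infusion | none | first PRONTO infusion |
| Placebo, yes | first PRONTO infusion | first extension infusion | first extension infusion |
| Placebo, no | first PRONTO infusion | none | none |

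Section 8 does not choose between these columns. For the OLE Safety Population, its extension-only data and visit window point to the first extension infusion. For the pooled set it uses the PRONTO windows for parent data and the extension windows for extension data, and each has its own Day 1.

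**Step 3. Size of the gap in a corrected pooled set with 8.11 unchanged**

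Inputs:

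- Protocol 4.1 requires a completed end-of-study visit in NEOD001-201 before entry.
- SAP Table 2 opens that visit's window at Day 320 (Month 12 low 295 + 30 − 5) and sets the target at Day 338.
- SAP 4.5 divides days by 30.4375 to give months.

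The first extension infusion cannot precede that visit. For a parent-placebo subject, the gap between the two origins is the PRONTO day of the first extension infusion minus 1:

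- Window low: 320 − 1 = 319 days; 319 / 30.4375 = 10.48 months.
- Target: 338 − 1 = 337 days; 337 / 30.4375 = 11.07 months.

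Illustration: two subjects, one from each parent arm, start the extension on PRONTO Day 338 and die on extension Day 100. That is PRONTO Day 338 + 99 = 437.

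| Rule | Parent NEOD001 | Parent placebo |
|---|---|---|
| 8.11 as written | 437 − 1 + 1 = 437 days (14.4 months) | 100 days (3.3 months) |
| First PRONTO infusion for both | 437 days | 437 days |
| First extension infusion for both | 100 days | 100 days |

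The two clinical courses are identical, yet 8.11 reports them 337 days apart.

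**The case against.** The strongest reply is that the 437 versus 100 day contrast is not what the plan produces. In the set as Section 5 defines it, the first study drug and the first NEOD001 infusion coincide, so that wording difference is harmless. The contrast appears only if the set is enlarged and 8.11 is left alone. This is correct, and the example should be read that way. Section 8 does, however, require the placebo subjects, so a correction to Section 5 alone would lead straight to it.

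Several narrower points have some force:

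- The Day 1 rule in SAP 4.1 sits among reporting conventions and follows a sentence about listings. Carrying it into 2.3.2.6 is one reading, though nothing in the SAP excludes it.
- The parent study was randomized (Protocol 1.3), so the reference in 8.2.1 has a meaning for pooled data. It has none for the extension (Protocol 3.4), and 8.2.1 does not say which set it covers.
- Tables 2 and 3 carry a footnote to the baseline definition, so the intended baseline can be found. The loose wording does suggest that NEOD001 sometimes stands for parent study drug generally. That makes its use in the definition that selects subjects more doubtful.
- Dropping the Placebo column would also remove the contradiction, and the set's name favours that reading. It would go against both 7.1 and 8 and lose the planned display. SAP Section 10, which lists the analyses cut when the program ended, mentions no such removal.

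The impact is limited. The Section 8.6.3 model has no treatment term, survival is tabulated by Kaplan-Meier without a test, and the OLE Safety Population outputs are unaffected.

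**Conclusion.** The concern holds, and the plan should be corrected. The population contradiction is certain from the text: Placebo N=0 and Overall equal to NEOD001. The SAP also fails to give the pooled set one survival origin. With the set corrected and 8.11 unchanged, each on-schedule parent-placebo subject's survival time would be at least 319 days (10.5 months) shorter than from the first PRONTO infusion, and 337 days (11.1 months) shorter at target.

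That bound assumes the end-of-study visit required for entry is the end-of-study visit (EEOS) of Table 2, and that the subject reached the Month 12 infusion on schedule. An earlier visit would shrink the gap. The number of PRONTO placebo deaths left without an origin cannot be derived from the documents.

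Only descriptive outputs on the pooled set are affected. Renal and NIS-LL outputs are affected only if Section 8's instruction to present them in the same way carries the restriction over. The adverse event layout in SAP Table 6 uses All Treated Subjects and is unaffected.

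**What to change.** 1. In SAP 5, define the pooled set as all subjects who received any amount of study drug, NEOD001 or placebo, in NEOD001-201, displayed by treatment received there. A name without NEOD001 in it would avoid the same confusion later.
2. Exposure (SAP 9 and 9.1) is summarized on the same set, so show it by treatment received or restrict it to NEOD001 infusions.
3. State one survival origin per set: the first study drug infusion in NEOD001-201 for every column of the pooled set, and the first extension infusion for the OLE Safety Population. Put this in Section 8 and align 2.3.2.6, 8.2.1 and 8.11 with it, replacing the reference to randomization in 8.2.1.
4. In Tables 2 and 3, anchor PRONTO Baseline to the first parent-study drug infusion, as 2.2.4.1 does.

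Items 1 and 3 should be made together, because item 1 alone creates the mismatch in survival time. The cost is SAP wording only; no new data are needed.
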